Data security.

Electronic data will be stored on a local ECHCS server within the VA firewall. Electronic data will also be stored in REDCap, which meets VA security requirements for data collection and

storage. Data will only be able to be retrieved from within the VA network. Files will be user-restricted and/or password protected so that only members of the research team can access the data. [Any data administered on laptops will be done on VA laptops that meet the VA standards for encryption, anti-virus protection, and firewall security.]

The UCD Anschutz Campus CCTSI REDCap may also be used to facilitate data collection. The UCD Anschutz Campus REDCap is hosted by the Colorado Clinical and Translational Sciences Institute (CCTSI). Data collected or stored for this study that is placed on the CCTSI REDCap Database will not be accessed or used for any other study or purposes, and will only be accessed by VA-credentialed personnel. The CCTSI REDCap Database is a highly secure, nationally-utilized data management system, and it is housed within the highly-secure environment at the University of Colorado Denver. In specific, the UCD Anschutz Campus CCTSI REDCap may be used to facilitate online data collection or reminders to facilitate data collection. If the Veteran chooses to provide their email address or telephone number to facilitate online data collection throughout the study, the email address or telephone number may be shared with Twilio, a secure Cloud application that facilitates data collection for CCTSI REDCap. No other identifying information will be shared, stored, or collected via Twilio. Specifics regarding this will be outlined in the postcard consent.

Electronic data may also be stored on a centralized research data repository such as the VA Informatics and Computing Infrastructure (VINCI). To ensure the protection of Veterans' data, VINCI maintains compliance with the guidelines set forth by Veterans Health Administration (VHA) Handbook 1200.12, Use of Data and Data Repositories in VHA Research and all other applicable VA and VHA policies and regulations. In addition, VINCI has undergone all security certification activities in support of obtaining an Authorization to Operate (ATO).

An approved videoconferencing platform will be used as necessary given developments with the COVID pandemic. Guidelines provided by the VA for maximizing data security will be followed.

Related to the EMA procedures, all data will be collected from a mobile application (Esmi). If participants wish to take part in the EMA assessment portion of the study, they will download and install the EMA app on their personal mobile device (e.g., phone or tablet). In the event that participants do not have a compatible mobile device they will be offered the option to borrow a study iPod (and complete the VA equipment loan form FL_10-219). If the participant does not have a compatible mobile device and does not wish to borrow a study iPod they will not take part in the EMA assessment portion of the study. Furthermore all participants will be notified in the postcard consent that: "Participation at all assessment time points is voluntary. If you choose to answer questions by audio recording or if you include identifying information in your responses, it is possible that mobile device could contain information that would identify you. These data will remain on your mobile device until you provide it to the VA research team. If you would like to avoid including identifying information or voice recording, you may do so. It is important that you understand that we cannot guarantee the security of the information you enter into your mobile device while it is in your possession. At the end of the week period, you will bring your phone or tablet to the study team so that your data can be stored securely behind the VA firewall

and then erased from your device.” Data will be uploaded at weeks 2 and 13 to a password protected, secured database behind the VA firewall. If contact restrictions prevent participants from meeting with a study team member to provide EMA data, the participant will be given the opportunity to provide these data at a later time after the contact restrictions have been lifted.

Similar procedures to the EMA application proposed in this protocol (e.g., audio recordings) have been utilized and IRB approved through both the National Center for PTSD/Stanford University and through a Rocky Mountain MIRECC study (COMIRB# 16-0109). For additional details regarding use of the study iPods and transfer of data to the VA Network please see the “iPod Baseline” and “iPod Standard Operating Procedure.” These documents have been reviewed and approved by VA Office of Information Technology mobile technology specialists from Endpoint Engineering, Solution Delivery.

Audio files and transcripts. The research team will transcribe EMA audio recorded data and qualitative interviews related to the intervention. Audio files and transcripts will be saved and/or labeled in their entirety with the corresponding UI.

Paper data. All data will be stored within VA ECHCS. Paper data will be stored in locked filing cabinet(s) in a locked office in the MIRECC. Existing consent and HIPAA forms will be stored separately in locked cabinets, separate from participant data (i.e., measures, transcripts).

Aggregate data. Aggregate data with all PHI removed may be shared with collaborators outside of the VA. However, appropriate data sharing agreements and memorandums of understanding will be put in place prior to sharing any data.

Staff training. Procedures designed to maintain confidentiality and data security will include training of all study personnel in regard to data security, research ethics, and study procedures, as well as formal mechanisms for limiting access to all information that can link data to individual participants.

VI. Potential Scientific Problems:

Clinical pilot studies are a critical first step in investigating the utility and value of conducting a full-scale RCT because they provide an opportunity to identify and respond to potential scientific problems. Recruitment for an intervention on moral injury could prove difficult. To buffer against recruitment challenges, we will recruit across outpatient clinics, community based outpatient clinics, and Veteran centers. We have consistently been able to recruit Veterans for clinical ACT-MI groups and have strong working relationships with the PTSD Clinical Team (PCT-MI), Substance Abuse Treatment Program (SATP), and Mental Health Clinic ([name] is a clinician in the PCT-MI and SATP). These clinics are enthusiastic about ACT-MI and administrators expect that they will be able to support the proposed study. Our patient flow from FY2017 also supports our sample size. However, if necessary, we will also mail potential participants directly based on review of their medical records.

A rigorous evaluation of the efficacy of ACT-MI will require a relevant and potent active control condition. PCT-MI was selected as the comparison condition for several reasons. First, we chose to compare ACT-MI to an active control rather than a waitlist control as this methodology was not acceptable to referring clinics (would delay Veteran care). Second, in the efficacy study it will be important to determine if potential gains are due to the intervention's specific attributes rather than nonspecific effects which a waitlist control would not facilitate. Third, treatment as usual (particularly a transdiagnostic intervention) does not yet exist for moral injury as moral injury interventions are still relatively new. A criticism of PCT-MI in comparison to ACT has been identified based on the equivalent results of Lang and colleagues' (2017) study comparing ACT and PCT-MI. [name], one of our Co-I's was also Co-I on the Lang study and identified significant methodological limitations associated with this study. [name] reported that therapists on the Lang study were trained in both ACT and PCT-MI, which has the potential to contaminate PCT-MI with ACT based principles. Once learned, ACT may be a particularly difficult therapeutic framework to ignore for the sake of applying a different intervention as ACT therapists are taught to target a behavior's function above and beyond other intervention strategies. The possibility for ACT principles extending to the control intervention is particularly relevant for PCT-MI, as PCT-MI is a semi-structured intervention, which provides therapist latitude. We believe that a critical safeguard in differentiating ACT from PCT-MI is in hiring experienced therapists for the PCT-MI condition who do not have a history of training in ACT. Additionally, the Lang study did not adequately assess and address competency in delivering the ACT intervention. Drs. [name] and [name] will work with the study team as well as review tapes of the sessions to ensure fidelity and competency. PCT-MI has the potential to be a strong comparison condition for ACT-MI in a future efficacy trial given its transdiagnostic structure, group format, and because it is currently been investigated in Litz and colleagues' ongoing Adaptive Disclosure efficacy trial.

Another barrier that was apparent in reviewing the literature was in the measurement of moral injury. To address this barrier our team developed a moral injury interview to help facilitate screening for Veterans to ensure appropriateness for participation in the study. We are taking a multidimensional approach to assessing moral injury to ensure that our measures are sensitive enough to capture changes in functioning. We will be administering measures related to ACT processes repeatedly (e.g., AAQ-II, MEAQ-30) over the course of treatment to help determine which measures might be most sensitive to change over time for a future efficacy trial. Additionally, we will be using EMA via the implementation of a mobile application to measure changes associated with functional outcomes and ACT processes in a more ecologically valid manner. We have consulted with an expert in EMA who has previously collaborated with the Palo Alto VAMC to identify how to utilize a mobile application to detect changes in moral emotions, experiential willingness, and behavioral activation ([name]). EMA procedures have been successfully applied to measuring in the moment changes in emotions in Veterans⁹⁴ and have also been used to assess experiential avoidance and shame, indicating the relevance and feasibility of this methodology to the goals of the present study.⁹⁴⁻⁹⁵ Please see the "measures" section for more details about EMA procedures.

VII. Data Analysis Plan:

Data Analysis & Methodological Considerations. Analyses will be descriptive in nature, although variability and precision estimates (95% confidence intervals) will be provided for

acceptability and feasibility summary statistics. Results will be presented across participants and individually for each group. **Sample Size.** Areán and Kraemer recommend sample sizes between 50 and 100 to generate variability estimates for outcome measures and to facilitate a “dress rehearsal for the clinical trial” (p. 95).¹⁷ As this trial serves as a precursor to a larger scale efficacy study and one of our goals is to determine the fit of candidate outcome measures, we will enroll 36 participants per condition (72 participants total) to account for attrition. As a method of data analysis for qualitative measures, thematic content analysis will be used as an iterative process of interpretation for the purposes of scoring, coding, and seeking patterns (themes) across verbal materials so that inferences about characteristics of a group can be generated.^{97, 5} First, data will be recorded and coded without identifiers. Reviewers will independently code interviews. Each interview will be coded by at least two reviewers. Reviewers will independently identify themes among codes. Reliability and validity among themes between reviewers will be determined in a consensus meeting. In the consensus meeting the coding team will define and name the themes that best represent the narratives from the individual interviews. This process is consistent with previous qualitative research conducted on moral injury.⁵

Aim 1: Evaluate the acceptability of the ACT-MI intervention for Veterans experiencing impairment in functioning associated with moral injury. We will assess the proportion of participants who find ACT-MI acceptable, defined as $\geq 70\%$ of participants scoring ≥ 24 on the Client Satisfaction Questionnaire (CSQ).¹⁹ The Narrative Evaluation of Intervention Interview (NEII)²⁰ will be used to inform any necessary revisions to the intervention and refinement of the treatment manual. Qualitative data collected using the NEII will be used to understand the limitations and strengths of the interventions via thematic content analysis. If fewer than 70% of participants find ACT-MI or PCT-MI acceptable, the qualitative data will be examined to determine areas for improvement.²⁰

Aim 2: Determine the feasibility of the efficacy study design. Feasibility will be assessed by examining the following outcomes related to recruitment, retention, and provider adherence **a) Participant recruitment rates.** The number of participants approached for the study who are eligible to participate and of those, the number who enroll in the study (i.e., willingness to participate) will be evaluated. Feasibility will be defined as $\geq 50\%$ eligible and of these $\geq 30\%$ willing to participate in the proposed time frame. **b) Participant Retention.** Participant completion of ACT-MI will be measured by the percentage of participants who complete treatment and receive an adequate dose (completed a minimum of 70% of the intervention). Reasons for termination will be examined via the RT-C/T. The percentage of participants lost to follow up (LTFU) will be calculated as the percentage of participants who fail to complete one-month and three-month follow-up visits, with $\leq 30\%$ LTFU considered feasible. This will inform the necessary sample size and treatment retention strategies for future studies. **c) Provider adherence.** To examine the extent to which ACT-MI can be delivered as intended ($\leq 15\%$ of deviations for each clinician across participants on the treatment fidelity checklist), the proportion of sessions in which each clinician achieved acceptable fidelity out of all of the clinician’s sessions will be reported for all study clinicians. Qualitative review of fidelity checklists will be used if treatment fidelity is less than desired and areas of difficulty will be identified to inform training procedures for clinicians and treatment manual revisions.

Aim 3: Select measures and calculate necessary sample size for a future efficacy study. Evaluate candidate measures based on the following factors: (1) Amount of missing data and its distribution for all measures across groups; (2) means, standard deviations, and 95% confidence

intervals for all measures within and across groups; and (3) correlations and 95% confidence intervals between a self-reported clinically significant change measure and candidate measures across groups. Missing data and frequency distributions will be examined to identify measures that have the least amount of missing data, and the extent of outliers or other anomalies. Means and standard deviations will be examined to identify and exclude measures with limited sensitivity to change due to ceiling or floor effects, or restriction of range.⁷⁷ Finally, higher correlations between participants' scores on the Global Ratings of Change Scale and the candidate measures will suggest that these measures are more sensitive to clinically significant change. Confidence intervals will be examined to determine how much to emphasize these findings when selecting measures. The study team will work closely with [name] in considering these various statistics and their limitations when selecting the most promising outcome and mediational measures for the future efficacy study.

After the primary outcome measure has been selected, we will calculate the necessary sample size for the efficacy study. This will require an estimate of variability and effect size in the target sample. We will estimate variability across groups at baseline and the variability of change scores on the outcome measure. The estimate with the greatest variability will be used in our power calculation because it will provide the most conservative (i.e., largest) estimate of the necessary sample size. Unlike estimates of variability that can be based on the entire sample, estimates of effect sizes are limited by the group sizes. Increasingly, methodological experts argue against the use of pilot data to estimate effect sizes because of limitations related to sample size and protocol/intervention changes, leading to invalid estimates. Instead, best practice is to set the effect size in power calculations to whatever value is considered minimally clinically significant.¹⁷ We will use the available literature and consultation with experts on measures of functioning when selecting this effect size and calculating the necessary sample size for the efficacy study.⁶⁷

Aim 4 and Aim 5: The analyses described above for Aim 1 and Aim 2 will be replicated using data collected from Veterans who participated in the intervention and study remotely (i.e., using videoconferencing and REDCap).

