used at the Palo Alto VAMC (n = 14 Veterans)¹⁵ and the Denver VAMC (n = 22 Veterans completed; n = 4 current cohort). These initial groups have informed early iterations of the ACT-MI manual. [name] and the team integrated manuals across sites and began using the manual included in this proposal as part of the treatment offered at the Denver VAMC. Program evaluation data have been collected. Acceptability data was collected in the most recent ACT-MI cohort at the Denver VAMC (n = 5 Veterans) that [name] and [name] co-facilitated. All five Veterans rated the intervention to be well above the Client Satisfaction Questionnaire (CSQ) acceptability cutoff of ≥ 24 with scores ranging from 30 to 32-points. In particular, all Veterans endorsed “yes, they helped a great deal” when asked, “have the services you received helped you to deal more effectively with your problems?” All Veterans also reported “yes definitely,” when asked, “if a friend were in need of similar help, would you recommend the program to him or her?” Another measure of acceptability we administered was the Narrative Evaluation of Intervention Interview (NEII). Below are responses to items from the NEII in each content domain (responses from each patient are included).

Table 2. Acceptability Data from most recent ACT-MI Cohort

Content Domain of NEII	Patients' Responses
Description of the intervention process “What change, if any, took place during participation in the intervention? If a change did not take place, please describe what happened during participation in the intervention?” “How does this intervention differ from other interventions you attended in the past?”	“My change was acceptance. I am not admitting what happened was right but that it happened and is in the past.” “I have got myself out of isolation.” “I am not alone.” “The way I look at things. Now I’m bigger picture.” “Increase in self-esteem.” “This one worked on the pain and not the memory.” “More direct input and ideas from others.”
Description of the intervention outcome “Please describe what the intervention contributed to you. What was its impact after the intervention was completed?”	 “It helped me feel much better about who I am as a person.” “Gave me ideas of how to move forward in life and how to make sense of the pain.” “It started with me forgiving myself.”

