Inclusion Criteria: 1) Eligible for VHA care (information obtained from review of medical record), 2) Age 18-89 (information obtained from review of medical record), 3) Has been deployed to a warzone (information obtained from Veteran self-report/screening interview), 4) Has experienced a morally injurious event which continues to interfere with functioning (information obtained from Moral Injury Events Scale [MIES], Moral Injury Questionnaire-Military Version [MIQ-M], and self-report/screening interview), and 5) Willing to be randomized and participate in either of the two conditions (information obtained from Veteran self-report/screening interview). 6) When groups are only being offered through videoconferencing, participants will need a computer/smartphone capable of accessing the VA approved videoconferencing platform in a private setting.

Exclusion Criteria: 1) Inability to demonstrate understanding of the postcard consent (as evidenced by inability to respond correctly to postcard consent questions or medical record review), 2) Inability to complete study measures (e.g., due to significant acute intoxication/withdrawal symptoms, mania, psychosis, aggression, catatonia, cognitive impairment) (results of veteran self-report, screening, or discretion of interviewer), 3) Imminent suicide risk (medical record or UWRAP), 4) Membership in a vulnerable population (e.g., pregnant women) (medical record or self-report), 5) History of significant violence towards VA staff (medical record), 6) Participation in another psychotherapy research study, (medical record

or self-report), and 7) Current participation in an EBP for a condition related to moral injury (medical record or self-report).

C. Study Design and Research Methods

Design: We are proposing a two arm, randomized, controlled pilot study to assess the feasibility of a future randomized clinical trial (RCT) evaluating the efficacy of ACT-MI. Candidate measures for a future efficacy trial will be administered at baseline, post-treatment, and one- and three-month follow-ups. Measures of acceptability will be administered following treatment completion/discontinuation. Veterans who are eligible to receive treatment at the VA ECHCS and who are eligible and interested in participating in the study will be enrolled and randomized to: (1) Present Centered Therapy (PCT-MI) or (2) ACT-MI.

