Preliminary Screening. Preliminary screening will occur in person or by telephone. After detailed information about the study is shared, potential participants will be given the option to provide verbal consent and complete a verbal screening interview based on inclusion and exclusion criteria. Research personnel will also review the Veteran's medical records to further evaluate study eligibility. Following the screening, potential participants will be scheduled for their Baseline Assessment. Their appointment may also be confirmed via text message. ***Baseline Assessment Session and Randomization.*** Baseline assessment sessions will be conducted in person when possible. When necessary, baseline sessions will be conducted online using REDCap and telephone/videoconferencing. A waiver of consent and HIPAA are being requested to allow for a consent process with a postcard consent rather than a formal physical signed consent form. After demonstrating understanding of the postcard consent and indicating willingness to participate, participants will complete the safety measure (UWRAP) and then assessment measures (SCID-5 modules, C-SSRS, VLQ, PROMIS, OQ-45, PHLMS, AAQ-II, AAQ-II past week MEAQ-30, MEAQ-30 past week, CFQ-MI, CFQ-MI past week, PHLMS, PHQ-9, PCL-5, E-MIS, AUDIT, BAM-R and ASIQ). Participants and the study assessor will be blind to condition. At the conclusion of the assessment session, participants will be randomized to ACT-MI or PCT-MI. The study biostatistician will predetermine group assignment through block randomization to ACT-MI or PCT-MI (block size = 4); stratified to condition based on previous participation in an Evidence-Based Psychotherapy (EBP). We chose to stratify participants based on past EBP participation as we believe previous treatment engagement could significantly impact responsiveness to treatment and thus want to ensure that the groups are as evenly distributed as possible based on this variable. We felt this was more important to prioritize than stratifying for diagnosis given the transdiagnostic nature of the proposed intervention. Randomization results will be concealed in a sealed envelope until the end of the baseline assessment session. ***Treatment Participation.*** Participants randomized to either ACT-MI or PCT-MI will complete the intervention in an outpatient context. When necessary, ACT-MI and PCT-MI will be conducted over a VA approved videoconferencing platform. The treatments will be delivered across twelve group sessions. Investigators will attempt to offer treatment as quickly as possible, however, this will be dependent on group start dates. Participants will

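### The exclusion criteria do not bar Veterans who have already had ACT-MI, although up to 26 received it at the Denver site; how many would enrol, and which way they would move the acceptability result, is unknown

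*Combined protocol and SAP*

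**What the plan says.** Section IV.B lists seven exclusion criteria. Two concern other therapy: no. 6, "Participation in another psychotherapy research study", and no. 7, "Current participation in an EBP for a condition related to moral injury". None names ACT-MI, and no. 7 reaches only therapy in progress.

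Section III (Preliminary Studies) reports earlier use of ACT-MI: 14 Veterans at Palo Alto and, at Denver, "n = 22 Veterans completed; n = 4 current cohort". The manual in the proposal later came into use "as part of the treatment offered at the Denver VAMC", and program evaluation data were collected.

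The Recruitment part of section IV.C takes referrals from the PTSD Clinical Team, the substance abuse program, the Mental Health Clinic and other providers, and adds targeted mailings. Section VI states: "We have consistently been able to recruit Veterans for clinical ACT-MI groups and have strong working relationships with the PTSD Clinical Team".

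Allocation is in blocks of four, "stratified to condition based on previous participation in an Evidence-Based Psychotherapy (EBP" (section IV.C, Baseline Assessment Session and Randomization). Section VI wants PCT-MI therapists without ACT training because "Once learned, ACT may be a particularly difficult therapeutic framework to ignore".

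Section VII sets 36 participants per condition and the Aim 1 rule of at least 70% with CSQ of 24 or more. It repeats the Aim 1 and Aim 2 analyses for remote participants under Aims 4 and 5. No analysis separates Veterans who have had ACT-MI before.

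**The concern.** As written, a Veteran who finished a clinical ACT-MI group and still has impaired functioning can meet every inclusion criterion and no exclusion. That Veteran can be randomised to either arm.

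In the ACT-MI arm, a repeater rates a treatment already experienced, so the Aim 1 proportion and the Aim 2 completion rate may not describe first-time participants. In the PCT-MI arm, a repeater brings ACT skills into the comparison groups. The plan takes ACT carry-over seriously enough to restrict who delivers PCT-MI, but has no matching safeguard for who receives it. It also gives the possible effect of previous treatment on response as its reason for stratifying, so it accepts that treatment history matters.

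**Working it through.** **1. Do the criteria reach prior ACT-MI?** No. 6 concerns research studies. The Denver groups are described as treatment with program evaluation, so it does not clearly apply. No. 7 is limited to current participation. Inclusion 4 requires continuing interference with functioning, which removes recovered Veterans but not all previous participants.

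**2. Size of the pool.** 22 + 4 = 26 at Denver. The plan's total reproduces as 36 × 2 = 72, and 26/72 = 36.1%. This compares a ceiling with a target; it is not an expected share.

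**3. The Aim 1 rule at full enrolment.** 0.70 × 36 = 25.2, so 26 of 36 are needed. 26/36 = 72.2%, with an exact 95% interval of 54.8% to 85.8%.

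**4. How many satisfied repeaters turn a fail into a pass?** Assume every repeater scores 24 or more.
- n = 36, one: 24/35 = 68.6% becomes 25/36 = 69.4%, still a fail.
- n = 36, two: 23/34 = 67.6% becomes 25/36 = 69.4%, still a fail.
- n = 36, three: 23/33 = 69.7% becomes 26/36 = 72.2%, a pass.
- n = 30, one: 20/29 = 69.0% becomes 21/30 = 70.0%, a pass.
- n = 25, two: 16/23 = 69.6% becomes 18/25 = 72.0%, a pass.

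The smaller n are illustrations of attrition. Splitting in-person from telehealth data under Aim 4 also reduces the denominators.

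**5. Chance of meeting the rule.** With k repeaters, all satisfied, and a true rate p among new participants, the chance is P(X ≥ r − k), where X is Binomial(n − k, p) and r is the count needed. The values of k and p are assumptions.

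| n (r) | p | k = 0 | k = 1 | k = 3 | k = 5 | k = 8 |
|---|---|---|---|---|---|---|
| 36 (26) | 0.60 | 9.0% | 11.2% | 16.9% | 24.5% | 39.9% |
| 36 (26) | 0.65 | 23.4% | 27.2% | 35.7% | 45.5% | 61.6% |
| 36 (26) | 0.70 | 46.6% | 51.0% | 59.9% | 68.8% | 80.9% |
| 25 (18) | 0.65 | 30.6% | 35.8% | 47.4% | 60.1% | 78.7% |

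The expected proportion moves by k(1 − p)/n. For k = 3, p = 0.65 and n = 36 this is 3 × 0.35/36 = 2.9 points, from 65.0% to 67.9%.

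**6. The opposite direction.** A repeater may be dissatisfied. At n = 36, 25/35 = 71.4% (pass) plus one dissatisfied repeater is 25/36 = 69.4% (fail).

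**7. Does stratification help?** It aims at similar numbers with previous EBP in each arm. The 70% rule is judged within the ACT-MI arm, so a balanced number of repeaters is still present in its denominator. The plan also does not say whether ACT-MI counts as an EBP. Section II describes ACT as evidence-based, while the Benefits text in section V says the efficacy of ACT-MI has not been evaluated.

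**The case against.** The case for leaving the plan alone has real weight.

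- **Other filters exist.** Continuing impairment, willingness to accept either arm, and a chart review and interview that consider appropriateness may keep some previous participants out. If ACT-MI is coded as an EBP, no. 7 bars the cohort then in treatment and past completers fall in the previous-EBP stratum. This stands, but staff discretion is not a rule and the coding is not settled.
- **The flips are edge cases.** Three repeaters in one arm imply about six enrolled under equal allocation, or 6/26 = 23% of the Denver pool. A shift of 2 to 3 points is small beside the interval in step 3. This stands.
- **Little hangs on the threshold.** Missing 70% leads to examination of the qualitative data, not to stopping. ACT-MI completion has no pass mark, and the pilot is not powered for efficacy. This stands and limits the importance of the point.

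A reader might also infer more than the documents support:

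- *Repeaters would inflate acceptability.* All five Veterans in the most recent cohort with CSQ data scored 30 to 32, but five scores give an exact 95% interval of 48% to 100% for the satisfied proportion. Anyone who returns must still be impaired and may have been disappointed.
- *The same clinics supplied the earlier groups.* Section VI mentions recruitment to those groups alongside its clinic relationships, but does not say who referred the 26.
- *All 26 used the manual under test.* Section III says initial groups informed early iterations and the present manual came later; it does not say how many received it.
- *Repeaters fall outside the efficacy trial's population.* That trial's eligibility is not given.

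**Conclusion.** The gap is real: no eligibility rule or planned analysis deals with previous ACT-MI, at a site where up to 26 Veterans received it as clinical care, some with the current manual. Stratification does not protect the within-arm 70% rule, and the safeguard against ACT carry-over covers therapists only.

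It would be wrong to conclude that the acceptability result will be distorted, or by 36%. The number who would enrol is not given and the direction is unknown. Upward bias is plausible but rests on five scores. A few repeaters matter less than sampling error. Near the threshold, one to three satisfied repeaters can change the reading depending on n, on the assumption that all of them score 24 or more. This is a cheap improvement to the plan, not a flaw that undermines it.

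**What to change.** Add to the exclusion criteria: *Previous or current participation in an ACT-MI group (clinical or program evaluation), from medical record or self-report.*

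If such Veterans have already been randomised, keep them in the study and identify them from records. Report the Aim 1 and Aim 4 CSQ proportions and the Aim 2 completion rate with and without them.

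The cost is a one-line amendment, checked in the medical record review already done at screening. At most about 26 Denver Veterans, plus any of the 14 from Palo Alto, leave the recruitment pool. Any who are approached and excluded would count as ineligible in the Aim 2 recruitment measure, so the reason should be recorded. The target of 72 does not change.
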